13.1 Risks Associated with an Ultrasound Scan

Ultrasound imaging is based on non-ionizing radiation and is generally considered safe when used by appropriately trained health care providers. Ultrasound energy has the potential to produce biological effects on the body and the waves can heat the tissues slightly. In some cases, it can also produce small pockets of gas in body fluids or tissues (cavitation). The long-term consequences of these effects are still unknown.

13.2 Risks Associated with Study Participation

The study involves use of an investigational software solution that allows users to communicate (by text, voice, screen share, webcam video and remote takeover) from an ultrasound system or workstation to a remote destination. The potential risks associated with use of Collaboration Live include interruption of the procedure due to poor connectivity or network performance and exposure of patient data by a remote user.

13.3 Risk Minimization Actions

According to the As Low As Reasonably Achievable (ALARA) principal a physician should expose the patients to ultrasound energy "As Low As Reasonable Acceptable" to perform an ultrasound diagnosis. Mechanical Index and Thermal Index are displayed on the image, and the Healthcare Provider is instructed to monitor those values and keep them to a minimum.

Study risks can be further minimized through compliance with this protocol, compliance with instructions for use (IFU), and performing procedures in the appropriate clinical environment by healthcare professionals per standard of care, specifically:

- Collaboration Live will only be used by those properly trained and qualified as required by the institution. The local system user remains responsible for patient safety while a Collaboration Live session is in progress.
- All Collaboration Live users should follow the applicable patient privacy and data security policies required by their country and institution.

Protocol		Document Title:	Protocol Date:	
Study Number:	10649	Collaboration Live Clinical Study	24Oct2019	Page 13 of 18

13.4 Anticipated Benefits

Subjects may not receive any direct benefit from participating in this study. Future patients may benefit due to image quality improvements in the ultrasound system.

14 Deviations

All non-compliance to protocol procedures shall be reported as a protocol deviation. The Principal Investigator is not allowed to deviate from the protocol unless prior approval from the Sponsor and the IRB is granted. Only protocol deviations made to protect the rights, safety and well-being of subjects are allowed without prior approval from the Sponsor and the IRB.

Examples of protocol deviations include, but are not limited to:

- Failure to obtain consent before scanning with the investigational system
- Enrollment of ineligible subject
- · If subject's images from the investigational system are used for primary diagnosis

All protocol deviations shall be recorded on the Protocol Deviation Form. Deviations that affect the rights, safety, and well-being of the subject must be reported within 24 hours to the Philips clinical monitor by the Principal Investigator.

15 Safety and Device Deficiency Reporting

Definitions for safety-related terms are included in Appendix 1 - Definitions.

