Study Design:	This is a prospective, single-arm clinical study of subjects who provide written consent. Subjects are scanned using a Philips EPIQ 5 or EPIQ 7 Ultrasound System equipped with Collaboration Live software. The study investigator will evaluate performance of the Collaboration Live tool with regard to performance of conferencing, sharing and control capabilities. Adverse events will be reported and the study investigator will assess potential relationship to the study device or study procedure. Additionally, the utility of Collaboration Live in remote consult of study patients will be evaluated. No patient follow-up beyond the initial consultation will be conducted with the Collaboration Live software solution.
Population:	30 subjects
Key Eligibility Criteria:	Subjects must be willing and capable of providing informed consent and participating in the study. Subjects must be indicated for a routine OB/GYN ultrasound examination at the site.
Sites:	1
Anticipated Study Duration:	3 months
Participant Duration:	Single visit (1 day)

4 Background Information

The Collaboration Live Clinical Study is intended to evaluate the performance and safety of the Collaboration Live software in a clinical setting and will enroll 30 patients scheduled for routine OB/GYN ultrasound exams. This is a prospective, non-randomized, single-arm clinical study. No patient follow-up is planned beyond the initial exam. The anticipated study duration is three months.

Ultrasound imaging is a form of medical imaging that involves the use of high frequency sound waves. Typically used to help a physician evaluate, diagnose, and treat patients, ultrasound imaging is minimally invasive and no radiation is involved. Collaboration Live is a software solution integrated into Philips EPIQ Ultrasound Systems that enables remote viewing, conferencing and control of the system. All study scanning (including scanning performed under remote control) will be conducted using the ALARA principle to ensure the safety of the subjects. As ultrasound imaging is based on non-ionizing radiation, it is generally considered safe when used by appropriately trained health care providers.

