The use of Collaboration Live as part of the study does not significantly alter the risk profile of the Ultrasound System. A description of study risks is presented in Section 13, Risk and Benefit Analysis. Under 21 CFR 812.3(m), the Sponsor requests IRB determination of the study as a Nonsignificant Risk (NSR) Device Study. There is no specific benefit to individuals participating in the study.

Protocol	ol	Document Title:	Protocol Date:	
Study Number:	10649	Collaboration Live Clinical Study	24Oct2019	Page 6 of 18

The ethical principles for the treatment of human subjects on this study have their origin in the Declaration of Helsinki.

This study will be conducted according to the IRB-approved study protocol, ISO 14155 Clinical Investigation of Medical Devices for Human Subjects and applicable regional/national regulations.

Institutional Review Board (IRB) review and approval will be obtained, prior to consent and enrollment of any subject, and dispense of any test article. Any additional requirements imposed by the IRB or regulatory authority will be followed, if appropriate.

5 Product Description

Collaboration Live is a nondiagnostic software solution intended for use with Philips (Philips Ultrasound, [name]) EPIQ and Affiniti Series Ultrasound Systems (software version 5.0.2) that allows users to communicate (by text, voice, screen share, webcam video and remote takeover) from an ultrasound system or workstation to a remote destination.

With Collaboration Live, users may:

- Get real-time remote technical and application support from Philips.
- Confer remotely with peers during an exam.
- Share screens.
- Activate remote control of the screen, touch screen, and control panel.

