5.1 Regulatory Status

The Collaboration Live software solution is considered investigational (i.e., has not been cleared by the FDA). For this study, the Collaboration Live feature will be evaluated as integrated into the EPIQ 5 and EPIQ 7 Ultrasound Systems (software version 5.0.2). The EPIQ Ultrasound Systems and supporting transducers used in the study have received FDA clearance and are indicated for use in obstetric and gynecological exams. The Philips EPIQ Ultrasound System is considered safe for use in human subjects in this clinical study because extensive safety testing has been conducted to confirm the safety profile and all hardware is FDA-cleared. The hardware complies with the following medical device safety standards listed in Table 5 below.

	Standard Name and Description
Electrical Safety	EN/IEC 60601-1:2006 + A1:2013 – Medical electrical equipment – Part 1: General requirements for basic safety and essential performance. The Philips EPIQ System has been designed and verified to comply with the electrical safety requirements of this standard, including requirements for electrical ground bond, leakage current, and dielectric withstand.
Electromagnetic Compatibility	EN/IEC 60601-1-2:2007 – Medical electrical equipment – Part 1-2: General requirements for basic safety and essential performance – Collateral standard: Electromagnetic compatibility – Requirements and tests. The Philips EPIQ System has been designed and verified to comply with the radiated and conducted emission requirements of this standard.
Usability	EN/IEC 60601-1-6:2010 – Medical electrical equipment – Part 1-6: General requirements for basic safety and essential performance – Collateral standard: Usability. The Philips EPIQ System has been designed and verified to comply with the usability requirements of this standard.

Table 5: Compliance with Medical Device Standards

Protocol		Document Title:	Protocol Date:	
Study Number:	10649	Collaboration Live Clinical Study	24Oct2019	Page 7 of 18

	Standard Name and Description				
Diagnostic Ultrasound Imaging	EN/IEC 60601-2-37:2007 – Medical electrical equipment – Part 2-37: Particular requirements for basic safety and essential performance of ultrasonic medical diagnostic and monitoring equipment. The Philips EPIQ System has been designed and verified to comply with the diagnostic ultrasound imaging requirements of this standard.				

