8.1.5 Ultrasound Exams: Remote Viewing and Remote Control

All subjects are indicated for a medically-necessary routine ultrasound exam and will undergo this exam as conducted by a qualified ultrasonographer. Using the Collaboration Live software installed on the ultrasound system, the study investigator will remotely view the exam, including images acquired, in real time. As necessary, the investigator may use the system's capabilities (including text, voice, screen share and webcam video) to provide feedback to the ultrasonographer. The investigator or delegates will also provide assessment regarding use of the Collaboration Live software on a 5-point (Likert) scale, including:

Protocol		Document Title:	Protocol Date:	
Study Number:	10649	Collaboration Live Clinical Study	24Oct2019	Page 9 of 18

- Streaming and image quality
- Ease of use
- Overall experience

The Collaboration Live software's remote control capability will also be used to adjust system settings during the exam. Systems settings may be adjusted by the investigator to assist in the following tasks:

- Image optimization (e.g., image depth, focal depth, gain)
- Pulsed-wave or Color Doppler Imaging
- M-Mode Imaging

To assess the primary endpoint, clinical acceptability, the investigator and qualified ultrasonographer will monitor the system response relative to input changes and record any adverse events occurring during remote control.

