Travel reduction attributable to use of Collaboration Live	Distance between the scanning facility and the investigator's location will be recorded (in miles).		
Ease of use	5-point (Likert) scale data will be reported by the investigator.		
User feedback regarding streaming, image quality and overall experience	5-point (Likert) scale data will be reported by the investigator.		

Table 11: Data Required for Assessment of Endpoints and Additional Measures

Protocol		Document Title:	Protocol Date:	
Study Number:	10649	Collaboration Live Clinical Study	24Oct2019	Page 12 of 18

Endpoint or Additional Measure	Required Variables
Patient feedback regarding remote consultation	Telemedicine Satisfaction Questionnaire ¹ (to be completed by subject following remote consultation).
Impact of remote consultation on reimbursement	Submitted charges and reimbursement rates for remote patient consultation will be reported and compared to standard rates for in-person consultation.

¹ Yip MP, AM Chang, J Chan and AE Mackenzie. Development of the Telemedicine Satisfaction Questionnaire to evaluate patient satisfaction with telemedicince: a preliminary study. Journal of Telemedicine and Telecare 2003; 9: 46-50.

12 Sites

This is a single site study being conducted at Perinatal Associates of New Mexico. The site includes multiple facilities under the direction of the Principal Investigator.

13 Risk and Benefit Analysis

The investigational systems have passed quality assurance testing according to international regulatory guidelines; therefore, the risk of using the device is no greater than the standard risk of using any commercially available ultrasound imaging equipment.

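### The travel measure records only a distance, so it counts miles as saved even if an in-person consultation is still needed; separately, a Section 14 deviation example is worded for the scanner when the software is meant

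*Protocol*

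**What the plan says.** **Travel.** Protocol Section 7.1 includes, among its additional measures, the reduction in travel that can be credited to Collaboration Live. Section 11 presents Table 11 as the place where the variables needed for the endpoint and the additional measures are specified. For travel, Table 11 gives one variable: the miles between the scanning facility and the investigator. Section 8.1.6 records the length of the remote consult and the miles between patient and consulting physician. Section 7 leaves the site's usual image review and in-person consultation in force where diagnosis requires them. Section 8.1.10 dismisses the subject after the scan, consult and questionnaire, with no follow-up.

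**Deviation list.** Section 14 gives as one example of a deviation that a subject's "images from the investigational system are used for primary diagnosis". Another example in the same list is "Failure to obtain consent before scanning with the investigational system". Section 13 states: "The investigational systems have passed quality assurance testing according to international regulatory guidelines". On regulatory status, Section 5.1 says "The Collaboration Live software solution is considered investigational", while the EPIQ systems and "supporting transducers used in the study have received FDA clearance". Section 5 adds that "Collaboration Live is a nondiagnostic software solution". The synopsis says "Subjects are scanned using a Philips EPIQ 5 or EPIQ 7 Ultrasound System equipped with Collaboration Live software", and Section 8.1.5 says "All subjects are indicated for a medically-necessary routine ultrasound exam and will undergo this exam as conducted by a qualified ultrasonographer".

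**The concern.** A distance tells us how far apart two people were. It becomes a saving only if someone would otherwise have travelled and did not have to. The protocol itself foresees that some subjects may still need to be seen in person, yet neither place that describes the travel data asks whether this happened. A total or mean of the recorded miles would then include journeys that were not avoided. The measure's name also claims a causal effect that a single-arm study with no record of usual-care travel cannot show.

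The Section 14 bullet raises a different and smaller matter. If the phrase means the scanner, a clinician who reads the subject's medically necessary exam in the ordinary way commits a deviation. A monitor applying the list as written could log routine care. The list also does not name the event that Section 7 is directed against, which is a diagnosis made from the remote view.

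**Working it through.** **1. The plan's own figure.** The only statistical figures in the protocol are the exact intervals of Table 16. For 30 acceptable exams out of 30, the two-sided 95% Clopper-Pearson lower limit is 0.025^(1/30) = 0.884, which matches the stated 88.4%. The other rows also reproduce, apart from differences of 0.1 point in two of them (26/30 and 25/30). No input to these intervals comes from the travel data or the deviation log. Sections 9.4 and 16 put all completers into the primary analysis, with no exclusion for deviations. Neither point can therefore move Table 16.

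**2. Travel: what is recorded against what is needed.**

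| Item | Section 8.1.6 | Table 11 |
|---|---|---|
| Distance | yes (patient to physician) | yes (facility to investigator) |
| Consult time | yes | no |
| In-person consultation still needed or held | no | no |
| Travel that usual care would have involved | no | no |

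Both places give a distance, and 0 of 2 give the status of an in-person consultation.

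Let d_i be the recorded miles for subject i, and let v_i = 1 if an in-person consultation is still needed or held, and 0 otherwise. The measure as specified sums d_i over all subjects. The miles that could have been avoided are at most the sum of d_i × (1 − v_i). The excess is the sum of d_i × v_i.

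The protocol gives no expected number of in-person consultations. To show the range, assume equal distances and let k of the 30 subjects have v_i = 1. The share of counted miles that is not a saving is then k/30:

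- k = 0: 0/30 = 0%
- k = 1: 1/30 = 3.3%
- k = 3: 3/30 = 10%
- k = 30: 30/30 = 100%

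These values of k are illustrations, not estimates. Even at k = 0 the sum is only an upper bound on travel avoided, because the last row of the table is empty: nothing shows that a journey would have been made without the software.

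**3. Deviation bullet: which reading the text supports.**

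- *Scanner reading.* The companion bullet speaks of scanning with the investigational system, and one scans with an ultrasound machine. Section 13 compares the investigational systems with commercial ultrasound equipment. In both places the term means the EPIQ.
- *Consequence.* The synopsis and Section 8.1.5 make the study scan on that EPIQ the subject's medically necessary exam. Section 8 rules out additional interventions, and no second scan on another machine is described. Under the scanner reading, diagnosis from the subject's only described exam is a deviation.
- *Software reading.* Sections 5, 5.1 and 7 treat only Collaboration Live as investigational and nondiagnostic, describe the EPIQ as cleared for OB/GYN use, and keep the site's standard image review.

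The literal words follow the first reading and the purpose follows the second. That is a wording conflict, and the intent can be recovered from the rest of the document.

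**The case against.** **On travel.** The CRF is not shown and may already ask about in-person consultation. Table 11 is not a closed list of everything collected, since consult time (8.1.6) and demographics (8.1.4) are recorded but absent from it. Billing data are to be evaluated, and the sponsor has access to source data, so an in-person consultation might be traceable later. The measure is descriptive, one of eight additional measures, with no test or threshold attached. All of this stands, and it rules out a stronger inference that a reader might draw: that the missing information could never be recovered. The documents do not support that. What remains is that Section 11 says Table 11 specifies the necessary variables, and for this measure it specifies only a distance. The protocol also does not say that billing or source records will be used to identify in-person consultations.

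It is also fair to say that a yes/no item does not prove that a trip would otherwise have occurred, and that an answer given at dismissal can miss a need that arises afterwards. Both limits are real. The item removes the clearest false count and does no more, which is why the measure's label should change as well.

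**On the deviation bullet.** Sections 5 to 7 make the intent plain to anyone holding the whole protocol. The list is expressly non-exhaustive, and all non-compliance is reportable, so a diagnosis made from the remote view could be caught without its own bullet. This stands too. A reader might infer that the protocol forbids clinical diagnosis from the study exam, or that all 30 subjects will be logged as deviations. The documents do not support either: Section 7 expressly keeps the site's standard image review in place.

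**Conclusion.** Both points hold as minor ones, and the travel point carries more weight. As specified, the travel measure would count miles as saved for any subject who still needs an in-person consultation. It cannot support a claim of reduction caused by the software, because usual-care travel is not observed and there is no comparator. The size of the overcount cannot be given from the protocol and may be zero. This conclusion assumes that the data are collected as Section 8.1.6 and Table 11 describe; if the CRF already holds the item, only the counting rule and the label need attention.

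The Section 14 bullet is a wording error and not a design flaw. Its practical risk is confined to inconsistent deviation logging, and no analysis depends on it.

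**What to change.** 1. Add one yes/no item to the travel row of Table 11 and to the CRF, answered when the subject is dismissed: *in-person consultation with the investigator still needed or held for this exam*.
2. Count the recorded distance only when the answer is no. Report the result as *potential travel avoided*, and drop the attribution to the software. State that needs arising after dismissal are not captured.
3. Reword the Section 14 bullet to: *if the primary diagnosis is made from images viewed remotely through Collaboration Live*.

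The cost is one extra CRF field for 30 subjects and two small text changes (the measure's label and the bullet). No subjects, visits or procedures are added.

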15.1 Routine Reporting

Subjects should be evaluated for AEs from the time Informed Consent Form is signed until conclusion of study-related activities. Documentation of the outcome of all safety events, assignment of relatedness, and seriousness is the responsibility of the Principal Investigator

All AEs (including AE, SAE, ADE, SADE or USADE) and Device Deficiencies occurring during the study are to be recorded on the Adverse Event CRF as soon as possible following awareness of the event.

The Investigator is responsible for reporting AE to the appropriate IRB as dictated by the guidelines defined by the IRB.

15.2 Expedited Reporting

All SAEs must be reported to Philips within 24 hours of the Investigator becoming aware of the event.

Additionally, any medical device deficiencies that might have led to a SAE if:

- suitable action had not been taken;
- intervention had not been made; or
- circumstances had been less fortunate

must also be reported to Philips within 24 hours of the Investigator becoming aware of the event.

Furthermore, any new findings or updates in relation to previously reported SAE or device deficiencies which may have potentially led to SAE must be reported to Philips within 24 hours of the Investigator becoming aware of the new findings or updates.

16 Statistical Methods

Continuous variables will be summarized using the number of non-missing observations, mean, standard deviation (SD), median, minimum, and maximum; categorical variables will be summarized using the frequency count and the percentage of subjects in each category. No formal statistical hypothesis test is planned and the primary endpoint will be presented as descriptive statistics only.

Protocol		Document Title:	Protocol Date:	
Study Number:	10649	Collaboration Live Clinical Study	24Oct2019	Page 14 of 18

The Primary Endpoint is clinically acceptable performance of remote control functionality. A total of 30 subjects undergoing routine OB/GYN exams will be enrolled in the study. Clinical acceptability of the Collaboration Live software will be evaluated for each subject during remote control of the ultrasound system.

A way to describe the statistical properties of the study design is in terms of 95% confidence interval of the true rate of clinical acceptability based on the observed data. Table 16 provides the two-sided 95% confidence interval (CI) for the true rate of clinical acceptability among 30 enrolled subjects using Clopper-Pearson Exact method. If clinical acceptability is observed in all 30 patients, then the 95% exact two-sided lower confidence bound for the rate of such response in this population would be > 80% (with lower bound of 95% CI = 88.4%). Alternatively, it means if the observed acceptability rate is 100%, then the range of 88.4% - 100% will contain the true acceptability rate, with 95% probability.

Table 16: Ninety-five Percent Confidence Intervals for True Rate of clinical accepatability by Observed Acceptability Rate

N	Observed Acceptability Rate	95% CI for True Acceptability Rate
	30/30 (100%)	(88.4%, 100%)
	29/30 (96.7%)	(82.8%, 99.9%)
	28/30 (93.3%)	(77.9%, 99.2%)
30	27/30 (90.0%)	(73.5%, 97.9%)
	26/30 (86.7%)	(69.3%, 96.3%)
	25/30 (83.3%)	(65.2%, 94.3%)
	24/30 (80.0%)	(61.4%, 92.3%)

All subjects completing the study will be included in the primary endpoint analysis. No follow-up is required beyond the initial study visit and therefore, no loss to follow-up or withdrawal is anticipated. However, if subject withdraw were to occur prior to evaluation of clinical acceptability, additional subjects will be enrolled to compensate for the withdrawn subjects. The study will end when 30 subjects have been enrolled and data collection is complete. The anticipated study duration is three months.

17 Labeling

The investigational device(s), the instructions for use, or the packaging shall indicate that the investigational device(s) is exclusively for use in a clinical investigation, as required by national regulations.

18 Direct Access to Source Data/Documents

A unique source record will be available for each study participant including documentation of the informed consent form review process, HIPAA completion to ensure patient privacy (United States), and medical history. In some cases (e.g., user feedback data may be entered directly into the CRFs, as appropriate. The sponsor will be allowed access to source data to ensure compliance to the protocol.

The investigator(s)/institution(s) will permit study-related monitoring, audits, IRB review, and regulatory inspection(s) by providing direct access to source data/documents.

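### Do the 95% probability sentence and three last digits in Table 16 misstate what 30 subjects can show?

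*Protocol*

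**What the plan says.** Protocol section 16 (Statistical Methods) fixes the size: "A total of 30 subjects undergoing routine OB/GYN exams will be enrolled in the study". It plans no inference: "No formal statistical hypothesis test is planned and the primary endpoint will be presented as descriptive statistics only". Precision is described through Table 16, introduced thus: "Table 16 provides the two-sided 95% confidence interval (CI) for the true rate of clinical acceptability among 30 enrolled subjects using Clopper-Pearson Exact method". The table runs from 30/30 down to 24/30.

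For the best outcome, all 30 acceptable, the section says that "the 95% exact two-sided lower confidence bound for the rate of such response in this population would be > 80" per cent, and adds in parentheses "with lower bound of 95% CI = 88.4" per cent. It then restates this: if the observed rate is 100%, "then the range of 88.4% - 100% will contain the true acceptability rate, with 95% probability".

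The two rows of Table 16 in question are 26/30, printed as 69.3% to 96.3%, and 25/30, printed as 65.2% to 94.3%.

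**The concern.** Two things look wrong.

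First, the restatement conditions on an observed result and gives the resulting fixed range a 95% probability of holding the true rate. A Clopper-Pearson interval does not support that. Its guarantee concerns the procedure: over repeated studies at least 95% of such intervals cover the true rate. A probability for one realised range needs a prior, and the protocol states none.

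Second, the table names an exact method, yet three entries are not what that method returns for the printed counts.

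With no hypothesis and no power calculation, this paragraph and table are the only account in the protocol of what 30 subjects can show. Section 6 says the results may support regulatory submissions and publication. The worry is that the faulty sentence could be copied into a report, and that a correctly computed interval for 25 or 26 acceptable exams would disagree with the protocol's table.

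**Working it through.** **Inputs** (all from section 16): n = 30; two-sided 95%, so 2.5% in each tail; Clopper-Pearson; x = 24 to 30 acceptable exams.

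**Formulas.** Lower limit = 2.5% quantile of Beta(x, n − x + 1). Upper limit = 97.5% quantile of Beta(x + 1, n − x), or 100% when x = n.

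**Headline figure.** At x = 30 the lower limit reduces to 0.025^(1/30) = 0.8843, or 88.4%. This reproduces the protocol's figure, and it is above 80%.

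**Whole table.**

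| Count | Exact (%) | Printed (%) | Agreement |
|---|---|---|---|
| 30/30 | 88.43, 100 | 88.4, 100 | both |
| 29/30 | 82.78, 99.92 | 82.8, 99.9 | both |
| 28/30 | 77.93, 99.18 | 77.9, 99.2 | both |
| 27/30 | 73.47, 97.89 | 73.5, 97.9 | both |
| 26/30 | 69.28, 96.24 | 69.3, 96.3 | lower only |
| 25/30 | 65.28, 94.36 | 65.2, 94.3 | neither |
| 24/30 | 61.43, 92.29 | 61.4, 92.3 | both |

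Eleven of 14 limits agree at the printed precision. The other three differ by 0.1 percentage point.

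**Likely cause** (inferred; the protocol does not state it). Put the rounded rate times 30 in place of the count:

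- 0.867 × 30 = 26.01 gives 69.32% to 96.26%, which rounds to 69.3% and 96.3%.
- 0.833 × 30 = 24.99 gives 65.24% to 94.34%, which rounds to 65.2% and 94.3%.

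The same substitution in the other rows also returns the printed values, so all 14 limits are reproduced. Wilson, Agresti-Coull, Jeffreys and Wald intervals do not give the two discrepant rows. On this explanation the unrounded differences are:

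- 26/30 upper: 96.262 − 96.245 = 0.017 points
- 25/30 lower: 65.279 − 65.240 = 0.039 points
- 25/30 upper: 94.358 − 94.338 = 0.020 points

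They show only because each crosses a rounding boundary. The intervals themselves are 96.24 − 69.28 = 26.96 and 94.36 − 65.28 = 29.08 points wide.

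**The probability sentence.** At n = 30 the actual coverage of the procedure was between 95.7% and 99.7% at the seven true rates tried between 80% and 99%. That agrees with a guarantee of at least 95%. The probability that the rate exceeds 88.4% given 30/30 depends on the prior: 97.8% under a uniform prior, 99.4% under a Jeffreys prior, and 95.0% under a Beta(1, 1.46) prior. None of these is a figure the plan claims or uses. They show only that the sentence has no fixed probability to be right or wrong about until a prior is named.

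**The case for a change.** The case for a correction is that these are statements the protocol makes and gets wrong, so a later analysis plan would not make them right. The sentence is offered as the meaning of the interval, and it is the ready-made wording to copy if all 30 exams succeed. The 25/30 row cannot be excused as a rounding convention, since 65.28 and 94.36 do not round to 65.2 and 94.3. Repair would cost one sentence and three table entries.

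The factual part stands: the sentence is a misreading of a confidence interval, and the three digits are wrong. What does not stand is that this misstates the precision of the design. The only limits the section argues from are exact, as is every row from 27/30 to 30/30. It could also be said that the wording about a two-sided lower bound confuses a two-sided limit with a one-sided one. The parenthesis in the same sentence settles that, because it names 88.4% as the lower bound of the 95% CI. Nothing in the protocol says the illustrative sentence or table will be carried into the report.

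**Conclusion.** No change to the plan follows. The sentence is a common looseness in describing a confidence interval, and the table contains a clerical slip of 0.1 percentage point in three of 14 limits, against intervals about 27 and 29 points wide. The headline 88.4% and the comparison with 80% are correct.

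This rests on three features of section 16. The primary endpoint is reported descriptively, with no test or success threshold. The 25/30 and 26/30 rows are hypothetical outcomes that no other part of the protocol uses. Any interval in the final report would be computed from the observed count, so software would return the exact limits whatever Table 16 prints; this last point is an assumption about ordinary practice. If a success criterion were later tied to a Table 16 limit in one of those two rows, the digits would need to be exact. As written, correcting them or rewording the sentence would leave the sample size, the analysis and the conclusions as they are.
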